#### Prevention of Risks

All Lipiflow and iLux treatments will be performed by the same clinician who received training by each manufacturer's representatives. Both instruments have the current firmware available as of September 2019.

#### Adverse events

After each treatment and the subject having had an opportunity to spontaneously mention any problems, the Investigator should inquire about adverse events. All adverse events will be recorded on a separate adverse events form.

#### Benefits

- 1- Unblocking of inspissated meibomian glands
- 2- Improvement in dry eye symptoms – tearing, itching, redness

## **Participant Recruitment and Informed Consent**

### Recruiting

Subjects will be recruited from the Phoenix Eye Care patient population seen for dry eye evaluations.

### Informed Consent (*Sterling IRB- Informed Consent Document Preparation service requested*)

Patients must have the study explained to them by a member of the study team, they must be provided enough time to consider their participation in the study and provided an opportunity to ask questions of the study team. Subjects must sign the most current version of an informed consent form (ICF) written and approved by an Institutional Review Board (IRB). All patients who sign an ICF are considered enrolled subjects in the study and will not undergo any study-specific assessments until after they have signed the ICF. Subjects may withdraw their consent to participate in the study at any time, for any reason. The study investigator may also withdraw subjects from the study at their discretion in order to protect the rights, safety, or welfare of the subject. All withdrawn subjects will be included in study analyses, but they will not be replaced. No missing data will be imputed.

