### Total Number of Participants to be Enrolled:

The clinical site will enroll up to 42 subjects to ensure that 38 subjects have evaluable data for both treatments. With 38 evaluable subjects, this study will have 80% power to detect a half point difference between treatments on the 5-point Likert-style questionnaire, assuming within patient standard deviation of 0.75 points and at a significance level of 0.05.

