### Study visit (approx. 100 min)

1. Perform slit lamp evaluation to verify no abnormal clinical findings prior to treatment
2. Perform either bilateral Lipiflow or bilateral iLux per Screening visit randomization
3. Patient fills out 5 Point Likert Scale questionnaire about treatment received
4. Perform slit lamp evaluation to verify no abnormal clinical findings prior to treatment
5. Perform the other bilateral Lipiflow or bilateral iLux procedure  $\geq$  1-hour after first
6. Patient fills out 5 Point Likert Scale questionnaire about treatment received
7. Patient answers final Patient Preference Question

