#### Criteria for subject withdrawal by investigator

Subjects may be withdrawn from study treatment at any time if, in the opinion of the Investigator, continued treatment poses a risk to the subject.

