#### Statistical Analysis Plan

Descriptive statistics will be provided to summarize each treatment questionnaire response: N, mean, standard deviation, minimum, maximum, and median. Categorical or binary endpoints will be summarized by count and percentage. Other statistical tests of correlation, variance, or regression to be recommended by statistician and methods used will be reported in the final report.

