### **Risk / Benefit assessment**

#### Risks

- 1- Eyelid irritation, redness, or inflammation
- 2- Ocular irritation, redness, or inflammation
- 3- Ocular symptoms – tearing, itching, redness, temporary visual blur

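### Does the plan need a rule for a subject who completes only the first device's questionnaire?

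*Combined protocol and SAP*

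**What the plan says.** Four parts of the combined protocol and SAP bear on this.

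- **Informed Consent:** "All withdrawn subjects will be included in study analyses, but they will not be replaced. No missing data will be imputed".
- **Total Number of Participants to be Enrolled:** the enrolment target reads "The clinical site will enroll up to 42 subjects to ensure that 38 subjects have evaluable data for both treatments". The 80% power claim is tied to those 38.
- **Statistical Analysis Plan:** "Descriptive statistics will be provided to summarize each treatment questionnaire response", with N, mean, SD, range and median. Categorical endpoints get counts and percentages. Any further test is left to the statistician, with the methods disclosed in the final report.
- **Study visit:** after the first questionnaire and before the second device, the fourth step is "Perform slit lamp evaluation to verify no abnormal clinical findings prior to treatment". The last step is "Patient answers final Patient Preference Question".

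Stopping between devices is possible. The Risks section lists "Ocular irritation, redness, or inflammation", and Criteria for subject withdrawal by investigator says: "Subjects may be withdrawn from study treatment at any time if, in the opinion of the Investigator, continued treatment poses a risk".

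**The concern.** A subject who stops between the two devices has one questionnaire, no second questionnaire and no preference answer. On its face the plan treats this subject in two ways. The Informed Consent section keeps every withdrawn subject in the analyses, while the sample-size section counts only subjects with data on both devices.

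Three analyses could each claim to follow the text: a difference of device means over all observed scores, a paired comparison that drops the subject, and a model that uses every observed score. They need not give the same number. The trial is open-label and the choice of test is left to the statistician, so the choice could in principle be made after the scores are known. The preference percentages raise the same question, because the non-answerer may or may not be in the denominator.

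If stopping were common and related to discomfort, the reported device difference could depend on a choice that was never written down.

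**Working it through.** **1. Reproduce the plan's sample size.** The inputs, from Total Number of Participants to be Enrolled, are a difference of 0.5, a within-patient SD of 0.75 and a 0.05 significance level (taken as two-sided, since the sidedness is not stated). The SD of a paired difference is 0.75 × √2 = 1.061. A paired t-test with n = 38 has 80.8% power, so the stated 38 reproduces as complete pairs.

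**2. Power after losses.** With the same inputs:

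| Complete pairs | Power |
|---|---|
| 42 | 84.7% |
| 41 | 83.8% |
| 38 | 80.8% |
| 37 | 79.7% |

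The allowance is 42 − 38 = 4 subjects. Only a fifth loss, from any cause, takes power below 80%, and then by 0.3 points.

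**3. Chance that the case arises.** The documents give no rate of stopping between devices, so p is assumed. Among 38 subjects, the chance of at least one is 1 − (1 − p)^38: 31.7% at p = 1%, 53.6% at 2% and 85.8% at 5%.

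**4. Worst single subject.** Suppose one such subject scores 1 on a device that the other 37 score at mean m. That device's mean falls by (m − 1)/38, which is 0.066 for m = 3.5 and 0.079 for m = 4.0. The standard error of the difference is 1.061/√38 = 0.172, so the gap between the two estimates is 0.38 to 0.46 standard errors. This takes the lowest possible score and is an extreme case.

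**5. Average bias.** The following was simulated with 2,000,000 subjects per setting. Underlying means were 3.5 and 4.0, the within-patient SD was 0.75, and the within-subject correlation was 0.3 or 0.5. Scores were rounded to the 1–5 scale (true difference after rounding 0.440 to 0.464) and device order was 1:1. Stopping depended either on a low first score (1 or 2) or on an irritation level unrelated to the error in that score. Ranges are over the two correlations.

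| Stopping rate and cause | Difference of device means | Paired difference |
|---|---|---|
| 2%, low score | +0.003 to +0.004 | −0.010 to −0.006 |
| 2%, irritation | +0.012 to +0.017 | −0.001 |
| 5%, low score | +0.008 to +0.010 | −0.026 to −0.016 |
| 5%, irritation | +0.023 to +0.030 | −0.002 |
| 9–10%, low score | +0.015 to +0.021 | −0.048 to −0.034 |
| 10%, irritation | +0.033 to +0.043 | −0.005 to −0.004 |

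The largest entry, 0.048, is 0.048/0.172 = 0.28 standard errors. A model using all observed scores stays within 0.04 throughout. With equal devices and 5% stopping, every estimate is within 0.002 of zero.

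The ranking of the methods depends on the cause of stopping. If irritation shares half of the first-score error (a further assumption), then at 10% stopping and correlation 0.3 the paired bias is −0.035 and the device-mean bias +0.024. No single set is best in every case.

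**6. Preference percentages.** If x of 37 answerers choose a device, adding one non-answerer to the denominator changes the percentage by x/37 − x/38 = (x/37)/38. This is at most 1/38, or 2.6 points. Counts are planned alongside percentages, and the counts for the three answer options sum to the number who answered, so a reader can rebuild either version.

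**The case for a change.** The strongest case for a change is that including withdrawn subjects without imputation answers only part of the question. It puts the subject in one device's mean but does not say which estimate is the trial's result. Nor does the 10% allowance in Study Design / Methods / Procedures cover the case, because it is placed at screening. Everyone who signs consent counts as enrolled, so a literal reader might even divide preference counts by all 42. With an assumed 24 subjects choosing one device, that gives 57.1% (24/42) where 38 answerers give 63.2% (24/38). A few sentences would remove the choice at almost no cost.

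It is true that no section names the set or the denominator, and that a choice after the data are seen is possible. The practical force is limited. Both devices are used in one visit of about 100 minutes, and the slit lamp step does not itself say that a finding cancels the second treatment. N is reported with each mean, so unequal device totals would be visible. The 42-subject denominator needs four subjects with no answer to be counted as if they had been asked, and the printed counts would show it.

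The obvious remedy is also not a clear gain. Making complete pairs the main set gives the most biased of the estimates when stopping follows a low first score (−0.048 against +0.015). It also leaves withdrawn subjects out of the main comparison, against the Informed Consent wording.

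**Conclusion.** The gap is real but is one that analysts fill sensibly, and no change to the plan follows. The two statements serve different purposes: "to ensure that 38 subjects have evaluable data for both treatments" sizes the trial, while the Informed Consent section says whose observed data are kept. Both can be honoured by reporting each device's observed scores with their N and comparing devices by whatever test the statistician names. A paired test uses complete pairs and a model uses all scores, so the set largely follows from the test. That no between-device test is named is a separate and larger matter.

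The size is small: average bias below 0.05 points at stopping rates up to 10%, about nil with equal devices, at most 2.6 percentage points per preference non-answerer, and power above 80% unless more than four of 42 subjects are lost. These figures rest on assumed stopping rates, correlations and causes of stopping, and on a two-sided test. The conclusion would need another look if stopping between devices proved much more common than 10%.

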### Costs to Participants

Patients will receive treatments at no charge in exchange for participation in this study.

### Compensation to Participants

No compensation will be offered for participation.

## Lipiflow vs. iLux Patient Acceptance and Comfort Study Questionnaire

Subject Number:

Gender:

Date:

Time:

Bilateral Procedure 1: (Circle One)

Lipiflow

iLux

Q1 - This was a comfortable procedure.

1                      2                      3                      4                      5  
Strongly Disagree    Disagree            Undecided            Agree                Strongly Agree

Q2 - I would have this procedure again.

1                      2                      3                      4                      5  
Strongly Disagree    Disagree            Undecided            Agree                Strongly Agree

Q3 - I would recommend this procedure to my friends or family.

1                      2                      3                      4                      5  
Strongly Disagree    Disagree            Undecided            Agree                Strongly Agree

Q4 - My perception of the study doctor changed because of this procedure.

1                      2                      3                      4                      5  
More Negative        Slightly More Negative    Unchanged            Slightly More Positive    More Positive

Q5 - This was a Positive overall experience.

1                      2                      3                      4                      5  
Strongly Disagree    Disagree            Undecided            Agree                Strongly Agree

Subject Number:

Gender:

Date:

Time:

Bilateral Procedure 2: (Circle One)

Lipiflow

iLux

Q1 - This was a comfortable procedure.

1 2 3 4 5  
Strongly Disagree Disagree Undecided Agree Strongly Agree

Q2 - I would have this procedure again.

1 2 3 4 5  
Strongly Disagree Disagree Undecided Agree Strongly Agree

Q3 - I would recommend this procedure to my friends or family.

1 2 3 4 5  
Strongly Disagree Disagree Undecided Agree Strongly Agree

Q4 - My perception of the study doctor changed because of this procedure.

1 2 3 4 5  
More Negative Slightly More Negative Unchanged Slightly More Positive More Positive

Q5 - This was a Positive overall experience.

1 2 3 4 5  
Strongly Disagree Disagree Undecided Agree Strongly Agree

Final Question - Which procedure did you prefer?

(circle one)

Lipiflow

iLux

No Preference

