## **Study Design / Methods / Procedures**

This study is an open-label, single site, crossover trial comparing LipiFlow Thermal Pulsation System to the iLux System based on patient acceptance, comfort, and preference. The proposed sample size is 42 subjects allowing for 10% dropout during patient screening.

2 Visits: Screening visit and Study visit

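### The single preference item names the procedures by brand only, with LipiFlow always listed first, and randomising treatment order does not cancel a list-position effect (minor).

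*Combined protocol and SAP*

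**What the plan says.** The Study Design / Methods / Procedures section describes the design: "This study is an open-label, single site, crossover trial comparing LipiFlow Thermal Pulsation System to the iLux System". It names acceptance, comfort and preference as the bases of comparison. The last step of the Study visit section reads "Patient answers final Patient Preference Question", and the questionnaire prints that item as "Final Question - Which procedure did you prefer". The subject circles Lipiflow, iLux or no preference. The item does not mention which procedure came first.

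The two rating forms are built differently. The first is headed "Bilateral Procedure 1: (Circle One", followed by the two brand names, and the second has the matching heading for procedure 2. Both have fields for subject number, date and time. Lipiflow precedes iLux on both rating forms and on the final item.

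The Randomization section has each subject draw a slip that decides which device comes first. Nothing in the documents varies the order of the printed options. Nothing says who circles the device on the rating forms, or that the forms are reconciled with the draw.

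The Statistical Analysis Plan section promises counts and percentages for categorical endpoints and leaves any tests to the statistician.

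**The concern.** The strength of a crossover with randomised order is that effects tied to order, such as liking whichever procedure came last, average out across the two sequences. That protection covers only effects that depend on sequence. The printed position of a brand name is the same for every subject in both sequences, so any pull towards the first option adds to the LipiFlow count in both and does not average out.

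The second weakness is identification. A subject who has had two procedures at one visit, at least an hour apart, must attach each experience to a brand name. If the names are confused, the answer is reversed. Because the item carries no first or second label, the drawn sequence cannot reveal the error. Name confusion does not favour a device by itself; it shrinks a real preference. The two mechanisms should be kept apart: one shifts the result in a fixed direction and the other dilutes it.

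At stake is the reading of a named comparison that rests on one three-option answer from about 38 people.

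**Working it through.** **The plan's own figure.** The Total Number of Participants section states "With 38 evaluable subjects, this study will have 80% power to detect a half point difference between treatments", "assuming within patient standard deviation of 0.75 points and at a significance level of 0.05". Taking 0.75 as the within-patient SD, the SD of a within-subject difference is 0.75 × √2 = 1.061. With n = 38, the noncentrality is 0.5 / (1.061/√38) = 2.91. Two-sided noncentral t power at 0.05 is 80.8% on 37 degrees of freedom (80.7% on 36), and 38 is the smallest n that reaches 80%. The stated size reproduces. It concerns the Likert ratings; the plan makes no power claim for the preference item, so only n = 38 carries over.

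**Inputs for the preference item.** From the documents: n = 38, fixed option order, randomised treatment order. Assumed: all 38 choose a device; there is no true device preference; a share g circles the first-listed name regardless of experience; an exact two-sided sign test at 0.05 is used for illustration (the plan names no test).

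**Does treatment order cancel the shift?** Suppose 60% of subjects prefer whichever procedure came second (assumed) and the sequences are equal in size, 19 each. Without a list effect, the LipiFlow share is 40% in LipiFlow-first subjects and 60% in iLux-first subjects, and the mean is 50%: the period effect cancels. With Lipiflow always printed first:

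- g = 10%: 0.1 + 0.9 × 0.4 = 46% and 0.1 + 0.9 × 0.6 = 64%; mean 55%.
- g = 20%: 0.2 + 0.8 × 0.4 = 52% and 0.2 + 0.8 × 0.6 = 68%; mean 60%.

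A simulation with these inputs gave 55.0% and 59.9%. The list effect survives the balanced sequence.

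**What that does to a sign test.** With n = 38 the test rejects when 12 or fewer, or 26 or more, subjects choose LipiFlow. With no preference of any kind, the LipiFlow share is p = 0.5(1 − g) + g = 0.5 + g/2.

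| g (assumed) | LipiFlow share p | Rejection rate |
|---|---|---|
| 0% | 50% | 3.4% |
| 5% | 52.5% | 4.2% |
| 10% | 55% | 6.8% |
| 20% | 60% | 18.7% |

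At 10% and 20%, nearly all rejections favour LipiFlow.

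**Name confusion.** If the true split is 70/30 (assumed) and a share m reverses the names, the observed share is 0.7(1 − m) + 0.3m. For m = 5%, 10% and 20% this is 68%, 66% and 62%. Sign-test power is then 56%, 45% and 26%, against 66% at m = 0.

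**Does the proposed layout help?** Let the first-listed option be the first procedure and keep the 60% assumption. At g = 10% the LipiFlow share is 0.1 + 0.9 × 0.4 = 46% in LipiFlow-first subjects and 0.9 × 0.6 = 54% in iLux-first subjects; mean 50%. At g = 20% it is 52% and 0.8 × 0.6 = 48%; mean 50%. The shift is removed when the sequences are equal in size.

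**The case against.** The strongest reply is that neither mechanism is shown to operate. The trial is open-label. Each subject draws a slip bearing a brand name, and each rating form pairs a procedure number with the brand names straight after treatment. The preference item follows the second form, so most subjects should know which device was which. An undecided subject can circle no preference and need not fall back on the first name. The documents give no rate for either error. All of this stands and limits the likely size. It does not supply what the item lacks: a link to the procedure, or a balanced option order.

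A reader might infer more, namely that mislabelled rating forms also erode the Likert comparison on which the study is sized. The documents do not support that. The rating forms identify a procedure by its printed number and the subject number as well as by brand, and the draw fixes which device was procedure 1. A wrong circle can therefore be found and corrected, provided the draw is recorded. One wrong circle would leave a subject with two forms for the same device, which is visible on inspection. It is not stated that the subject does the circling, and list position cannot act on the Q1 to Q5 scores themselves. What remains there is a small procedural gap: no section requires recording the draw or checking the forms against it.

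**Conclusion.** The point holds for the preference item alone, as a minor, optional improvement. The only measure of a named comparison uses brand names in a fixed order, and the randomisation does not protect it against a list-position effect or against an untraceable reversed answer. The direction of a first-listed effect would be towards LipiFlow; its size cannot be found from the documents. The shares of 55% to 60% and rejection rates of 6.8% to 18.7% rest on assumed rates of 10% to 20%, on all 38 subjects choosing a device, and on a sign test that the plan does not specify. They show sensitivity and are not estimates of bias in this trial. The option order is read from extracted text; a side-by-side layout would still place Lipiflow first.

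**What to change.** Print the preference item in two versions, one per sequence, with these options: first procedure today (device name), second procedure today (device name), no preference. List position then follows the randomised order and is balanced across devices, and each answer is tied to a procedure the subject can place in time. Summarise the answers by sequence as well as overall, so that unequal sequence sizes among evaluable subjects can be seen.

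On the rating forms, have staff enter the device for procedures 1 and 2, record the draw, and check one against the other.

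The cost is one reprinted page and a short staff check. Sample size, visits and treatment do not change. The downside is that staff could pick the wrong version, so the version used must be checked against the recorded draw. If the data are already collected, reconcile the rating forms with the sequence where it was recorded, and report the fixed option order as a limitation of the preference result.
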